Behavioral economic methods can address these gaps in the literature [47-49] and measure the reinforcing and relative reinforcing efficacy of LCCs [50, 51]. One behavioral economic tool, the purchase task, measures hypothetical consumption of a product at escalating prices to calculate demand [52]. From this task, several demand indices can be assessed, including: (a) breakpoint (the first price at which consumption is zero), (b) intensity (consumption at the lowest price), (c) demand elasticity (sensitivity of consumption to cost increases) and cross-price elasticity (sensitivity of consumption of

one product to cost increases of another product), (d) Q_{\max} (maximum expenditure for cigarettes), and (e) P_{\max} (price at which expenditure is maximized) [49]. Products have greater addictive potential if their consumption is less sensitive to price (i.e., inelastic demand) [49]. The tool can also determine one product's substitutability for another product, that is, the change in the consumption of a product as the price of a second product increases (i.e., cross-price elasticity) [49]. The Cigarette Purchase Task (CPT) is a valid and reliable tool to measure cigarette demand, and its indices are associated with smoking behavior, dependence, and cessation [52-61]. However, its application to polyusers and to LCCs has been limited. Using an adapted version of the CPT, the proposed research will contribute to our knowledge of the addictive potential of LCCs compared with cigarettes among young adult regular dual users, and differences in those effects by flavor and sex. *This contribution will be significant because understanding the addictiveness of LCCs, how flavors influence their addictiveness, and if sex affects the addictiveness of LCCs and flavors will help public health practitioners develop cessation programs to better address tobacco addiction in high-risk populations, and policy-makers to regulate LCCs appropriately.* This research can markedly improve cessation rates in this high-priority group, and will inform regulatory and economic policy on cigars to discourage poly use. Increased cessation rates in young adults will significantly decrease their future morbidity and mortality.

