B. Innovation: (1) The emphasis on the addiction potential of LCCs within a polyuse context represents a new approach to the study of tobacco use in young adults. By explicitly addressing the relative reinforcing values of LCCs and cigarettes, the conditions under which substitutability occurs for this population can be studied in detail. (2) Use of behavioral economic methods to evaluate the addiction potential of LCCs relative to cigarettes is a methodological innovation. Current survey-based studies cannot address the relative addictive value of these products, or take into account the influence of flavorings. Laboratory methods to address these issues have been costly, and have not been able to adequately address the substitutability of LCCs for cigarettes. The CPT has several advantages over other methods including being relatively easy for participants to understand and researchers to implement, and not requiring costly and specialized equipment [62]. Moreover, it can be more sensitive to detecting changes in the relative reinforcing effects of a product than subjective measures [63], making it uniquely suited to study the effects of flavors in LCCs. (3) Advances in CPT methodology to study flavors can be applied to the study of other characteristics like nicotine content, and will inform future research and policymaking. As a new investigator, the results of the proposed research will enable me to write a follow-up R01 to investigate flavored vs. unflavored LCC addictive potential and the association with subsequent smoking behaviors measured in real-time. In addition, I can submit future R level applications to further modify the CPT to study other polytobacco use and other tobacco product characteristics that may contribute to polyuse.

Hypotheses, Aims and Objectives:

➤ Aims & Aim-Specific Hypotheses:

- Aim 1: To characterize the addictive potential of LCCs compared to cigarettes in dual users.
 - Hypothesis 1a: LCC demand elasticity will be higher and intensity lower than that of cigarettes, indicating less addictive potential of LCCs
 - Hypothesis 1b: The slope of the cross-price elasticity of LCCs and cigarettes will be positive and statistically significantly different from zero, indicating substitutability of LCCs as cigarette prices increase.

- Aim 2: To compare the addictive potential of preferred flavored vs. unflavored LCCs.

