- **Explain on what basis it is reasonable to assume that the sample size will be obtained:** Recruitment will take place over 18 months, requiring enrollment of about nine subjects per month. We will recruit from the community using flyers, subject referral, newspaper ads, radio ads, bus ads, and online sources like Craigslist.com. In [name] pilot study with African American young adult dual users (18-29), 63 participants were recruited in four months (~16 participants enrolled per month) using primarily Craigslist and subject referral (unpublished). Therefore, the proposed recruitment timeline is feasible.
- **Method(s) of data analysis:** Descriptive statistics including means (SDs) and frequencies (percentages) will be reported to describe demographic characteristics and smoking history.

From the CPTs, demand curves for LCCs (own brand, preferred flavor, and unflavored) and cigarettes will be graphically plotted, and consumption as a function of cost will be calculated using the Exponential Model of Demand [71, 72]. From the demand curves, the following indices will be calculated using standard equations [55, 72]: (a) breakpoint, (b) intensity, (c) elasticity and cross-price elasticity, (d) O_{\max} , and (e) P_{\max} . For Aims 1 and 2, the demand indices for own brand of LCCs, preferred flavor LCCs, unflavored LCCs, and cigarettes will be compared. In addition, the cross-price elasticity will be calculated using an extension of the exponential model of demand to determine how demand for LCCs (own brand, preferred flavor, and unflavored) changes as a function of cigarette price [73], adjusting for age, gender, race, and menthol status. Survey-based measures of LCC impressions, risk perceptions, and dependence will be calculated, compared by product using Analysis of Variance (ANOVA) tests, and correlations with demand indices will be examined. For Aim 3, the models will be stratified by gender to compare demand indices in women and men. In post-hoc analysis the demand indices will be stratified by race/ethnicity to detect any differences in the addictive potential of the products.

Subject Characteristics:

- Age: 18-34 years
- Ethnicity: All are eligible
- Gender: approximately 50% women and 50% men
- Vulnerable Populations: No special vulnerable populations (such as fetuses, neonates, pregnant women, children, prisoners, and institutionalized individuals) will be involved.
- Other characteristics: None
- Inclusion Criteria:

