 - **Minnesota Tobacco Withdrawal Scale-Revised (MTWS-R)** (previously called the Minnesota Nicotine Withdrawal Scale): to measure the withdrawal effects of smoking cessation as an assessment of nicotine dependence [77].
 - **Questionnaire of Smoking Urges (QSU)-Brief:** to comprehensively assess craving using 10 items that measure their thoughts and feelings about cigarette craving [78, 79]. It has been adapted to additionally ask about LCC craving.

- **Respiratory Form and Adverse Events log:** Subjects will rate potential adverse effects (cough, throat irritation, rhinitis, and mouth irritation, which have been noted in studies of cigarette smokers. We will assess symptoms on a 4-point scale: 0=absent, 1=mild, 2=moderate and 3=severe. Other AEs will also be recorded and severity rated.
- **Cigarette Evaluation Scale (CES):** to assess the subjective rewarding and aversive effects of cigarette smoking [80]. It has been adapted to additionally ask about LCC smoking.
- **Liking Survey:** to assess participants' likes and dislikes for foods, physical activity, common experiences, and tobacco products using a gLMS scale.
- **Cigarette Purchase Task (CPT):** to collect hypothetical consumption of cigarettes at escalating prices to calculate the demand breakpoint, intensity, elasticity and cross-price elasticity, O_{\max} , and P_{\max} [52, 55]. This is a measure of addictive potential of a product.
- **Cigar Purchase Task:** adapted from the CPT to ask about consumption of LCCs.
- **Cross-Price Purchase Task:** to collect hypothetical consumption of LCCs at increasing cigarette [49]. This will help to determine the substitutability of LCCs for cigarettes when cigarettes are prohibitively expensive.

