1) Risks of unauthorized disclosure of confidential material: Information about demographics, smoking history, current tobacco use, and risk perceptions will be collected about each participant. Data will be collected via paper forms and electronically, and stored electronically. There may be a small risk of unauthorized persons illegally accessing the data, but procedures will be in place to minimize this risk, including electronic data encryption and password protection, use of Qualtrics or REDCap for data management and storage (a secure cloud-based system), unique identifying codes and de-identification of the data, storage of hard copies of data in locked cabinets.

2) Burden of time to complete the research procedures: The procedures involved with data collection in this study require a moderate amount of time and multiple study visits.

3) Exposure to potentially stressful circumstances: Efforts to switch away from one's usual LCCs may be considered stressful by some participants.

4) Risks of smoking and toxicant exposure: Smoking is a significant risk factor for heart disease, cancer, respiratory disease, and many other health problems, and dual use may enhance those risks. Although we will choose a popular brand for the study-provided LCCs, they may not be the usual brand smoked by some participants. Because they vary in size and content, LCC brands vary in their levels of nicotine and toxicants. Therefore, the study-provided LCCs may increase some participants' nicotine and toxicant exposure compared to their usual brand.

B. Adequacy of Protection Against Risks

B1. Recruitment and Informed Consent. Community-based recruitment will take place using local media advertisements (newspaper, bus, radio), flyers, subject referral, and online sources (Craigslist.com). Participants will initially be screened over the phone. Those who are initially eligible will be scheduled for an in-person screening appointment (Visit 1). At Visit 1, potential participants will first provide a SAL to ensure they are able to take part in further procedures. If SAL \geq 10 mg/dL, one re-test will be allowed. If the individual still fails the SAL test, s/he will be deemed ineligible. If the SAL test is passed, potential participants will be given a thorough description of the study and asked to provide written informed consent. Next, basic inclusion/exclusion criteria will be assessed. Trained research staff or [name] will complete the consent procedures.

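### The intensity half of Hypothesis 1a compares cigarettes and LCCs without a common unit, so a difference in item size can produce the predicted result whatever the addictive potential

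*Combined protocol and SAP*

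**What the plan says.** Hypothesis 1a, under Hypotheses, Aims and Objectives, has two parts read together: "LCC demand elasticity will be higher and intensity lower than that of cigarettes, indicating less addictive potential of LCCs".

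Background A lists the demand indices and defines the second part as "intensity (consumption at the lowest price", with no unit. The same section ties addictive potential to price response: "Products have greater addictive potential if their consumption is less sensitive to price (i.e., inelastic demand".

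Study Procedures describes the Cigar Purchase Task only as "adapted from the CPT to ask about consumption of LCCs". Under Method(s) of data analysis, "consumption as a function of cost will be calculated using the Exponential Model of Demand", and for Aims 1 and 2 "the demand indices for own brand of LCCs, preferred flavor LCCs, unflavored LCCs, and cigarettes will be compared". No conversion to cigarette-equivalents, tobacco weight or nicotine is described. The covariates named there, for the cross-price analysis, are age, gender, race and menthol status.

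On item size the document points two ways. Background A describes LCCs as closely resembling cigarettes in size and shape. Protection of Human Subjects, A3, item 4 says: "Because they vary in size and content, LCC brands vary in their levels of nicotine and toxicants". The eligibility criteria do not restrict the participant's own LCC brand. Appendix A, item 1 gives as an example of the study product a brand that Preliminary Studies (1) classes as a cigarillo.

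**The concern.** A raw consumption figure compares reinforcing value between two products only if one unit of each means the same thing. If an LCC is the larger item, a smoker with identical demand for tobacco reports fewer LCCs than cigarettes at the lowest price. The plan would read that lower figure as less addictive potential. If the LCC is the smaller item, the error runs the other way.

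Breakpoint and P_max are prices per item, so a size difference shifts them in the opposite direction to intensity. The indices could then disagree on which product has more addictive potential with no true difference, and the plan has no rule for reading discordant indices.

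The protocol directs its findings to cessation programs and tobacco regulation, so the basis for any statement that LCCs are less addictive should not depend on how tobacco is divided into items.

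**Working it through.** **1. The plan's own figure.** Study Design gives d=0.5, two independent means, 80% power and alpha 0.10, hence 102, raised to 125 for 18% attrition. A two-sided two-sample t-test needs 51 per group, so 102 in total, with power 0.806; 102/0.82 = 124.4, rounded up to 125. Both figures reproduce. They concern the comparison by sex. The plan gives no alpha or test for the Aim 1 index comparison, so 102 and 0.10 are borrowed below for illustration only.

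**2. What item size does to each index.** The exponential model, for price C per item, is

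Q(C) = Q0 × 10^(k(exp(−αQ0C) − 1)).

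Let one LCC equal r cigarettes in tobacco, with identical underlying demand for tobacco. Then Q_LCC(C) = Q_cig(C/r)/r. Substituting gives the same model with the same α and k, and with Q0 replaced by Q0/r. Illustrative values (assumed, not from the documents) are Q0=12, α=0.003, k=2.5:

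| r | Intensity Q0/r | α | O_max | P_max | Point elasticity at $1 per item |
|---|---|---|---|---|---|
| 1.0 | 12 | 0.003 | 23.53 | 5.99 | −0.200 |
| 1.5 | 8 | 0.003 | 23.53 | 8.98 | −0.135 |
| 2.0 | 6 | 0.003 | 23.53 | 11.97 | −0.102 |
| 3.0 | 4 | 0.003 | 23.53 | 17.96 | −0.068 |

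Intensity falls as 1/r and P_max rises in proportion to r. The parameter α and O_max do not move. Point elasticity at a common per-item price does move: for r above 1 the LCC looks less elastic, which is against Hypothesis 1a.

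**3. How often the intensity leg would be met with no true difference.** Assume a paired t-test on log intensity with 102 pairs, counting significant results in the predicted direction at two-sided 0.10 (one-sided 0.05). The critical value is 1.660 on 101 df, and the noncentrality is ln(r)/SD × √102. The SD of the within-person log ratio is assumed to be 1.0, with range 0.75 to 1.5. Example: at r=1.25 and SD 1.0, 0.223 × 10.10 = 2.25, which gives 72%.

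| r | SD 1.5 | SD 1.0 | SD 0.75 |
|---|---|---|---|
| 1.0 | 5% | 5% | 5% |
| 1.1 | 16% | 25% | 36% |
| 1.25 | 44% | 72% | 91% |
| 1.5 | 86% | 99% | 100% |

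Because ln(0.8) = −ln(1.25), r=0.8 gives the r=1.25 row in the opposite direction: significantly higher LCC intensity in 44%, 72% and 91% of trials.

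**The case against.** The strongest reply is that Hypothesis 1a has two parts. A reader might infer from the table that item size alone could confirm the hypothesis. The documents do not support that: higher LCC elasticity is also required, and step 2 shows that size leaves α unchanged and moves same-price point elasticity the wrong way. This part of the reply stands in full. The percentages apply to the intensity leg only and are not false-positive rates for Hypothesis 1a.

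Second, a reader might infer that LCCs are larger than cigarettes. The documents do not say so. The risk section describes variation among LCC brands, and the only direct comparison with cigarettes, in Background A, calls them alike. This also stands: neither the size nor the direction of r is known. A loose resemblance does not settle the matter, though, since r=1.1 already raises the rate from 5% to between 16% and 36%. Own brands also vary between participants, whereas the calculation applies one r to everyone.

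Third, the purchase-task instruments are not reproduced, so a count of items is an inference. It is a reasonable one, as no other unit is given and the protocol's use measures count products.

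Fourth, all five indices will be calculated, so a pure size effect would show as lower intensity and higher P_max with unchanged α and O_max. That is true. But the plan does not say how such a pattern would be read, and the hypothesis names lower intensity as evidence of less addictive potential.

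**Conclusion.** The concern holds for the intensity half of Hypothesis 1a. Without a common unit, the cigarette-versus-LCC intensity contrast cannot separate reinforcing value from item size, and so is uninformative about addictive potential as planned. A modest size ratio is enough to dominate it: at r=1.25 the leg would be met in about 72% of trials (44-91%) with identical demand for tobacco. That figure rests on an assumed r, an assumed log-ratio SD, a paired test that the plan does not specify, and an alpha taken from the sex-comparison sample size.

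The elasticity half is unaffected if elasticity means the exponential-model α. The Aim 2 contrast of flavored with unflavored LCCs is largely free of the problem, because Appendix A provides for one brand for all participants. The sample size does not change.

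**What to change.** Amend Hypothesis 1a and Method(s) of data analysis as follows.

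- For the cigarette-versus-LCC contrast in Aim 1, base the addictive-potential conclusion on the exponential-model α and on O_max in dollars. State that elasticity here means α, estimated with the same k for both products, and not point elasticity at a common per-item price.
- Report cigarette-versus-LCC intensity, breakpoint and P_max as descriptive per-item figures, and state the unit.
- Keep intensity as a test index for flavored versus unflavored LCCs of the study brand in Aim 2.

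Dividing intensity by the participant's usual daily number of that product is not a good substitute. It removes the between-product difference in level: someone who smokes few LCCs and many cigarettes could score near 1 on both.

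The cost is a change of wording. Elasticity and O_max are already to be calculated, no new data are needed, and relying on α follows the plan's own criterion of price insensitivity. The one loss is that raw intensity no longer has a confirmatory role in the cigarette-versus-LCC contrast.

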 - Hypothesis 2a: Flavored LCC demand elasticity will be lower and intensity higher than that of unflavored LCCs, indicating greater addictive potential for flavored LCCs.
 - Hypothesis 2b: Cross-price elasticity of flavored LCCs and cigarettes will be positive and greater than the cross-price elasticity of unflavored LCCs and cigarettes, indicating greater substitutability of flavored LCCs.
- Aim 3: To explore sex-based differences in addictive potential of flavored and unflavored LCCs.
 - Hypothesis 3a: The addictive potential of flavored LCCs will be stronger in women than men, and the addictive potential of unflavored LCCs will be stronger in men than women, as measured by demand elasticity and intensity.
 - Hypothesis 3b: The substitutability of flavored LCCs will be greater among women than men and the reverse will be true for unflavored LCCs, as measured by cross-price elasticity.

See **Figure 1** for graphical representations of these hypotheses.

[figure not shown]

Figure 1. Hypothetical demand curves for cigarettes and LCCs (on a log-log scale). Panel A depicts the hypothesized self-reported demand for cigarettes and LCCs as the price for each product increases. It also depicts the hypothesized demand for LCCs as cigarette price increases (cross-price elasticity). Panel B depicts the hypothesized demand for flavored (FL) and unflavored (UNFL) LCCs, and the hypothesized cross-price elasticity of FL and UNFL LCCs for cigarettes. Panel C depicts the hypothesized demand and cross-price elasticity for FL LCCs among women (W) and men (M). Panel D depicts the hypothesized gender difference in demand and cross-price elasticity for UNFL LCCs.

Preliminary studies:

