- **Study design:** The study will employ a prospective, randomized cross-over design with 125 non-treatment-seeking young adult (18-34) dual users of cigarettes and LCCs. Using the original CPT and the CPT modified for LCCs, we will assess demand for cigarettes as cigarette price increases, demand for flavored and unflavored LCCs as prices for these products increase, and demand for flavored and unflavored LCCs as *cigarette* price increases across two study visits. Prior to each visit, participants will receive (in random order) their preferred flavor and unflavored LCCs to use at home to validate their responses on the CPT. Study visits will take place 7 to 10 days apart. This strategy has been used in our previous study of e-cigarettes and shown to be a sufficient time period to examine the impact of flavors on likeability of the product [64]. See **Figure 2**.

[figure not shown]

Figure 2. Randomized crossover study design

- **Sample size and justification:** We will enroll 125 non-treatment-seeking young adults (18-34) who are regular dual users of cigarettes and LCCs (see inclusion criteria for definition). Sample size calculation: No studies to date have investigated the main outcome for the proposed study: demand elasticity and intensity for flavored and unflavored LCCs, and cross-price elasticity of flavored and unflavored LCCs for cigarettes [65-68]. Published cross-price elasticities of LCCs for cigarettes range from 2.73 for little cigar sales [67] to 174.5 for cigarillo sales in exclusive, daily cigarette smokers [65]. Therefore, the sample size was calculated in G*Power 3 (94) using the standard medium effect size ($d=0.5$) for two independent means [69], in order to capture statistically significant differences by sex. With a sample size of 102, we can detect an effect size of 0.5 with 80% power and $\alpha=0.10$. In [name] pilot study with dual users [70], the attrition rate was 18%. Therefore, the final sample size of 125 participants will account for attrition.

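### Hypotheses 3a and 3b predict a sex-by-flavor interaction, but Aim 3 has only gender-stratified models, with no interaction term and no named between-sex test

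*Combined protocol and SAP*

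**What the plan says.** Under Hypotheses, Aims and Objectives, Aim 3 is "To explore sex-based differences in addictive potential of flavored and unflavored LCCs". Hypothesis 3a has two halves. The first is "The addictive potential of flavored LCCs will be stronger in women than men". The second half turns to the other product and predicts the opposite direction: "the addictive potential of unflavored LCCs will be stronger in men than women". Hypothesis 3b states the same pattern for cross-price elasticity: substitutability of flavored LCCs is expected to be "greater among women than men and the reverse will be true for unflavored LCCs".

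The analysis is one sentence under Study Design, Method(s) of data analysis: "For Aim 3, the models will be stratified by gender to compare demand indices in women and men". No test, interaction term or interval for the difference between the sexes is named there or elsewhere.

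Under Study Design, Sample size and justification, the trial is sized "using the standard medium effect size ($d=0.5$) for two independent means", and the reason given is "in order to capture statistically significant differences by sex". The power statement is that "we can detect an effect size of 0.5 with 80% power and $\alpha=0.10" at 102 participants, raised to 125 for 18% attrition. This is the only power statement in the document.

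**The concern.** A sex difference that changes direction with flavor is an interaction. The quantity that addresses it is the difference between women and men in the within-person flavored-minus-unflavored contrast. Fitting the models separately in women and men yields two sets of estimates, but by itself no test or interval for that difference.

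This leaves the readout of Aim 3 open. One way to fill the gap is to see in which sex the flavor effect reaches significance. The protocol reasons in this way from its own e-cigarette pilot (Preliminary studies, item 2), where an effect in women and none in men is taken to support a sex difference. Another way is to test women against men separately for each product. The first can produce or hide a sex difference by chance. The second tests two simple effects but not the interaction, and the stated power covers only one of those tests. What is at stake is the comparison that set the sample size.

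**Working it through.** **Inputs.** From Sample size and justification: d = 0.5, two independent means, 80% power, alpha 0.10, 102 evaluable, 18% attrition, 125 enrolled. From Subject Characteristics: about half women, so 51 per sex. From the crossover design: each participant gives a flavored and an unflavored value. Assumed, because the documents give no figure: the standardized paired flavor effect dz, the within-person correlation rho between the two products, and roughly normal indices.

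**1. The plan's own figure.** A two-sample t-test with d = 0.5 and two-sided alpha 0.10 needs 51 per sex, 102 in total, with power 80.6%. Sidedness is not stated; one-sided 0.05 gives the same 102, while one-sided 0.10 gives 74. Attrition: 102 / (1 − 0.18) = 124.4, rounded up to 125. Both figures reproduce, for one between-sex contrast of one index.

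**2. Strata compared by significance.** Let the true flavor effect be the same in both sexes and let p be the power of a paired t-test in 51 people. The chance that exactly one sex is significant is 2p(1 − p).

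| dz | p | exactly one sex significant |
|---|---|---|
| 0 | 0.100 | 18% |
| 0.1 | 0.183 | 30% |
| 0.2 | 0.408 | 48% |
| 0.25 | 0.547 | 50% |
| 0.3 | 0.680 | 43% |
| 0.4 | 0.880 | 21% |
| 0.5 | 0.970 | 6% |

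The error can also run the other way. If dz is 0.9 in women and 0.4 in men, both strata are significant with probability 88%, so the sexes look alike, while a direct test of the difference has 81% power.

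**3. Sexes tested directly for each product.** Let women exceed men by 0.5 SD for flavored LCCs and men exceed women by 0.5 SD for unflavored. Each test alone has 80.6% power. Hypothesis 3a needs both. At rho = 0 the chance is 0.806 × 0.806 = 0.65. By simulation it is 63%, 62%, 61% and 61% at rho = 0.3, 0.5, 0.7 and 0.8.

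**4. The interaction test.** Compare women and men on the within-person difference. Its SD is sqrt(2(1 − rho)) in units of one index's SD, so the standardized effect is the interaction divided by that SD.

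| rho | SD of difference | power, 0.5 SD interaction | power, 1.0 SD (full reversal) |
|---|---|---|---|
| 0 | 1.41 | 55% | 97% |
| 0.3 | 1.18 | 68% | 99.5% |
| 0.5 | 1.00 | 81% | >99.9% |
| 0.7 | 0.77 | 94% | >99.9% |

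The planned size therefore carries the interaction test at 80% if rho is about 0.5 or more, or if the full reversal is real. It does not if the interaction is 0.5 SD and rho is 0.3 or less.

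**The case against.** The strongest reply is that the Aim 3 sentence states a comparison of women with men, and that the sample size rests on two independent means. Together these point to a direct sex test for each index, not to a count of significant strata. Women and men are also independent samples, so a difference and its interval can be formed from two stratified estimates and their standard errors. This stands. A reader might infer that the plan settles Aim 3 by significance in one sex only, but the document does not say so. The fault is that the test is left unspecified. Under the favorable reading each sex test is valid for its own simple effect, and only the interaction remains untested.

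Two further inferences should be resisted. The 50% in step 2 is the maximum that 2p(1 − p) can reach, so it is not a typical rate. And setting 61–65% against 97% or more does not show that the interaction test gives more power for Hypothesis 3a as worded. A significant interaction does not establish both halves: a 0.5 SD sex difference in the flavored product alone also produces a 0.5 SD interaction. Both sex contrasts are still needed, and their joint power stays at 61–65%.

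A reader might also see a conflict in listing gender as a covariate of the cross-price model. That adjustment is described before the Aim 3 sentence, and the covariate simply drops out within a stratum.

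Finally, Aim 3 is worded as exploratory and no data are lost, since the crossover supplies the contrast. That lowers the weight but does not remove the point: the aim has directional hypotheses and supplied the rationale for the sample size.

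**Conclusion.** The concern holds in this form: Hypotheses 3a and 3b state a sex-by-flavor interaction, and the plan names neither a test of it nor a between-sex test of any kind. If strata are judged by significance, a common flavor effect appears in one sex only 6% to 50% of the time, depending on an effect size that the documents do not give. If the sexes are tested for each product, the chance of supporting both halves of Hypothesis 3a at d = 0.5 is about 61–65%, and the stated 80% applies to one contrast only. These figures assume 51 per sex, two-sided alpha 0.10 and roughly normal indices, with dz and rho shown as ranges. Because the aim is exploratory and the data will support the right analysis, this is a should-fix point.

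**What to change.** In Method(s) of data analysis, replace the Aim 3 sentence with the following plan.

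- For each index (elasticity, intensity, cross-price elasticity), fit one mixed model in all participants. Fixed effects are sex, flavor, sex-by-flavor, period, sequence and menthol status, with participant as a random effect. Keep the plan's age and race adjustment for cross-price elasticity.
- Test the sex-by-flavor term. Then report the women-versus-men contrast for flavored and for unflavored LCCs, with confidence intervals from the same model. State that both are needed to support the reversal as worded.
- Keep the gender-stratified demand curves as description.

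In Sample size and justification, state that the 80% is for a single sex contrast and give the sidedness of alpha. Add the interaction power under assumed correlations: 55% / 68% / 81% / 94% at rho = 0 / 0.3 / 0.5 / 0.7 for a 0.5 SD interaction, and 97% or more for a full 1.0 SD reversal.

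The cost is analysis wording only: no new data, visits or participants.
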